Currently there are no safety and immunogenicity data for the use of R21/Matrix-M™ in an Asian population. This trial will provide preliminary data to support a larger trial. For integration with the current Targeted malaria elimination (TME) activities, which provide mass drug administrations at months M0, M1, and M2, it would be most efficient and practical to provide the vaccine at the same intervals.

In summary: We propose to conduct a safety and immunogenicity trial of R21/Matrix-M™ in Thai adults. The major aims of this study are to: (1) assess the safety and immunogenicity of R21/Matrix-M™ in Thai adults, (2) confirm that the co-administration of antimalarial drugs with the malaria vaccine R21/Matrix-M™ does not reduce the immunogenicity of the vaccine, and (3) assess

**Research Proposal Submission Form
for a study involving human subject enrollment WITH
specimen collection**

Document No.: FTM ECF-033-01

Page 9 of 52

pharmacokinetics of antimalarial drug combination dihydroartemisinin/ piperaquine, and SLDPQ in subjects who concurrently receive R21/Matrix-M™.

B2. STUDY OBJECTIVES

B2.1 Primary Objective

- To assess the safety of the R21/Matrix-M™ vaccine, with and without concurrent anti-malarial administration, in Thai adults.

B2.2 Secondary Objectives

- To compare the immunologic response to R21/Matrix-M™ vaccine when concurrently given with DHA-PIP + SLD-PQ (Arm 1) with R21/Matrix-M™ vaccine alone (Arm 2) in Thai adults.
- To compare the piperaquine levels of participants who received the antimalarial drugs alone (Arm 3) with participants who received the antimalarial drugs combined vaccine (Arm 1).

B3. STUDY SITE(S)

Clinical study site:

This study will be conducted at the Clinical Therapeutics Unit (CTU), Hospital for Tropical Diseases, Faculty of Tropical Medicine, Mahidol University.

B4. STUDY TIMELINES:

We will recruit volunteers into this study after ethical approvals are granted from the Oxford Tropical Research Ethics Committee (OXTREC), and the Ethics Committee, Faculty of Tropical Medicine, Mahidol University. The volunteers will be included in this study for up to 7 months. We expect the recruitment period, data collection procedures, and to complete laboratory procedures and analysis approximately 18 months. The total duration for this study including preparations, regulatory approvals, and report writing is expected to be approximately 24 months.

B5. STUDY POPULATION AND SAMPLE

B5.1 Target population

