Vaccine and study medication accountability, storage, and handling will be in accordance with local SOPs. This study will not be blinded; i.e. it is an open-label study.

B6.2.2 Accountability of the study agents

The study site will maintain a record of the numbers of all vaccines and DHA/PIP + primaquine tablets obtained, used by the participants and returned to the pharmacy room in CTU. On study completion, a copy of the drug accountability record will be filed in the study folder.

B6.2.3 Concomitant medications

There will be no restrictions on concomitant medication beyond the exclusion criteria listed above.

B6.3 Study Endpoints

B6.3.1 Primary Endpoints

The safety of the investigational vaccine in each group:

- Occurrence of solicited from the date of each vaccination to 7 days of each vaccination.
- Occurrence of unsolicited adverse events (AEs) from the date of the first vaccination to 28 days after the last vaccination, according to the MedDRA classification.
- Occurrence of serious adverse events (SAEs) during the whole study period, i.e. during a 6-month follow up period from the receipt of first vaccination, according to the MedDRA classification.

B6.3.2 Secondary Endpoints

- For Arms 1 and 2, the concentration of antibodies against *Plasmodium falciparum* circumsporozoite (anti-NANP total IgG antibody), one month after the first dose (at Study month 1), one month after the second dose (at Study month 2), one month after the third dose (at Study Month 3) and six months after the first dose (at Study Month 6).
- Exploratory immunology endpoints including but not limited to cellular immunity.
- For Arms 1 and 3, piperaquine levels following the administration of the antimalarials with or without vaccine. (timepoints)

B6.4 Details of procedures for specimen/data collection

Procedures will be performed at the time points indicated in the schedule of procedures (Table 5). Additional procedures or laboratory tests may be performed, at the discretion of the investigators if clinically necessary (e.g. follow up repeat haematology or biochemistry laboratory tests in the event of clinically significant abnormal results).

Research Proposal Submission Form for a study involving human subject enrollment WITH specimen collection

Document No.: FTM ECF-033-01

Page 20 of 52

Table 5. Study Procedures

Timepoints	Month Day of month	Scr.	Study period																	
			M0				M1				M2				M3	M6 ^a				
			0 ^c	1	2	7	0	1	2	7	0	1	2	7	0	0				

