Document No.: FTM ECF-033-01

Page 23 of 52

be prepared by MORU statistician based on random numbers generated in STATA. The randomization sealed envelopes will be prepared by Clinical Trials Support Group (CTSG).

B6.4.4 Randomisation

Randomization numbers will be generated in blocks, for the 3 study arms in a ratio of 5:5:2, as follows:

- R21/Matrix-M™ + DHA-PIP+PQ (Arm 1)
- R21/Matrix-M™ alone (Arm 2)
- DHA-PIP+PQ alone (Arm 3)

Study participants will be assigned the next available randomization number on the list, and thus will be randomly allocated to Group 1, 2, or 3. This is an open-label study. Participants and clinical investigators will not be blinded to group allocation.

B6.4.5 First vaccination or anti-malarial medications initiation (Month 0 / Day 0 visit)

Participants in Group 1 and 2 will be vaccinated by intramuscular (IM) needle injection into the deltoid region of the arm. Participants in Group 1 will also receive anti-malarial medications. Participants in group 3 will receive anti-malarial medications only.

The study participants will be observed closely for at least 30 minutes following the administration of each study vaccine, with appropriate medical treatment readily available in case of an anaphylactic reaction.

An axillary thermometer, tape measure and a paper diary card for solicited AEs will be given to each participant along with the emergency 24-hour telephone number to contact the on-call study physician if needed. Diary cards will collect information on the timing and severity of the following solicited AEs (Table 8):

Table 8. Solicited AEs

Local solicited AEs	Systemic solicited AEs
Pain at injection site	Fever
Redness at injection site	Diarrhoea
Swelling at injection site	Nausea
Bruising at injection site	Vomiting
	Fatigue
	Headache
	Muscle pain (Myalgia)
	Joint pain (Arthralgia)
	Chills

Participants will be instructed on how to self-assess the severity of these AEs. There will also be space on the diary card to self-document unsolicited AEs, and whether medication was taken to relieve the symptoms.

**Research Proposal Submission Form
for a study involving human subject enrollment WITH
specimen collection**

Document No.: FTM ECF-033-01

Page 24 of 52

***B6.4.6 Subsequent vaccination (or subsequence rounds of anti-malarial medications) visits
(Month 1 / Day 0 and Month 2 / Day 0 visits)***

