DHA-PIP is the first line treatment for uncomplicated malaria in many malaria endemic countries in Asia and Africa and has an extraordinary robust safety profile (16-18). DHA-PIP is also very well tolerated. The main reported side effects are gastrointestinal upset (nausea, vomiting, abdominal pain and diarrhoea) as well as dizziness, headache and disturbed sleep. Rates of these side effects

Research Proposal Submission Form for a study involving human subject enrollment WITH specimen collection

Document No.: FTM ECF-033-01

Page 32 of 52

are generally < 10% and often <5% except for dizziness (~12%). There is no evidence that DHA-PIP can cause clinically significant QTc prolongation at therapeutic doses(19).

Primaquine (PQ)

Like all 8-aminoquinolones, primaquine is associated with haemolysis in G6PD deficient individuals in a dose-related relationship. To avoid any potential risk for haemolysis, participants will receive just a single low dose of primaquine (approximately 0.25mg/kg) on the day of vaccination, at each vaccine dose (for groups 1) and on Day 0 at each round of antimalarial drugs for three rounds (for group 3). This dose is safe even when administered to individuals with a genotype associated with severe G6PD deficiency(20). Other known side effects with primaquine administration include symptoms of gastritis and enteric complaints when administered for 14 days at large doses for the treatment of *Plasmodium vivax* malaria. Such abdominal complaints have not been observed when a single low dose primaquine is administered.

C2.2 Preventive and alleviative measures for risk

Phlebotomy

Participants' blood samples will be collected by well-trained medical personnel with aseptic technique to prevent infection or complications.

R21/Matrix-M™ vaccination

Volunteers will be vaccinated in a clinical area where Advanced Life Support trained physicians, equipment and drugs are immediately available for the management of any immediate post-vaccination serious adverse reactions. Participants will be observed closely for at least 30 minutes following administration of the vaccine. No SAEs attributable to the R21/Matrix-M™ were detected during the large trial in Burkina Faso.

Antimalarial medications

Dihydroartemisinin/piperaquine (DHA-PIP)

To exclude the possibility that pre-existing QTc prolongation results in AEs, the QTc of all volunteers will be measured and candidates with a QTc>450ms will not be enrolled.

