1.2.3 Solicited adverse events

Occurrence of solicited AE from the date of each vaccination to 7 days of each vaccination will be recorded.

Solicited local (injection-site) adverse events - The following local (injection-site) AEs will be solicited:

All age groups
Pain at injection site
Redness at injection site
Swelling at injection site
Bruising at injection site

Systemic solicited adverse events - The following general AEs will be solicited:

Adult
Fatigue
Fever
Diarrhoea
Nausea
Vomiting
Headache
Myalgia
Arthralgia
Chills

Note: Temperature will be recorded in the evening. Should additional temperature measurements be performed at other times of day, the highest temperature will be recorded in the CRF.

1.3 Clinical laboratory parameters and other abnormal assessments qualifying as adverse events or serious adverse events

In absence of diagnosis, abnormal laboratory findings (e.g. clinical chemistry, haematology, and urinalysis) or other abnormal assessments that are judged by the investigator to be clinically significant will be recorded as AE or SAE, if they meet the definition of an AE or SAE. Clinically

Research Proposal Submission Form for a study involving human subject enrollment WITH specimen collection

Document No.: FTM ECF-033-01

Page 41 of 52

significant abnormal laboratory findings or other abnormal assessments that are present at baseline and significantly worsen following the start of the study will also be reported as AEs or SAEs. The investigator will exercise his or her medical and scientific judgment in deciding whether an abnormal laboratory finding or other abnormal assessment is clinically significant.

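### The solicited-AE list covers four of the seven main DHA-piperaquine side effects named in C2.1 and omits dizziness, the only one put above 10%, so comparing dizziness between arms rests on unequal, unprompted reporting

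*Protocol*

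**What the plan says.** The primary objective (Protocol B2.1) is the safety of the vaccine "with and without concurrent anti-malarial administration, in Thai adults". The first primary endpoint in B6.3.1 reads: "Occurrence of solicited from the date of each vaccination to 7 days of each vaccination". Unsolicited AEs, from first vaccination to 28 days after the last, are the second.

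B6.4.5 gives every participant a diary card, Arm 3 included: "Diary cards will collect information on the timing and severity of the following solicited AEs (Table 8"). Besides four injection-site terms, Table 8 has nine systemic terms: fever, diarrhoea, nausea, vomiting, fatigue, headache, myalgia, arthralgia and chills. Appendix B 1.2.3 has the same nine under "Systemic solicited adverse events - The following general AEs will be solicited".

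On the drug, C2.1 says: "The main reported side effects are gastrointestinal upset (nausea, vomiting, abdominal pain and diarrhoea) as well as dizziness, headache and disturbed sleep". It adds that the rates of these effects "are generally < 10% and often <5% except for dizziness (~12" per cent).

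Anything not on the list is unsolicited. It reaches the data through free space on the diary (B6.4.5), diary review at visits (B6.4.7), AE assessment at visits (Table 5) and a non-leading question (Appendix B 1.4.3). The study staff grade it by CTCAE version 5.0 (Appendix B 1.5.1), whereas solicited events are self-graded on the diary scale.

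**The concern.** The objective asks about safety with and without the antimalarials. The diary card is the one safety instrument applied in the same way, with the same prompts, in all three arms. The drug effect that the protocol itself rates as commonest is not on it.

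Its comparison between arms then depends on what participants volunteer. Opportunities to volunteer differ by arm in an open-label trial: Arms 1 and 3 are seen on Days 1 and 2 of each round, while the drug is being taken, and Arm 2 is not. At stake is how far the tolerability comparison between Arm 1 and Arm 2 can be trusted for the effects most expected from adding the drug.

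**Working it through.** **1. Lists side by side.**

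| Main DHA-PIP effect named in C2.1 | In Table 8 and Appendix B 1.2.3? |
|---|---|
| Nausea | yes |
| Vomiting | yes |
| Diarrhoea | yes |
| Headache | yes |
| Abdominal pain | no |
| Dizziness (about 12%) | no |
| Disturbed sleep | no |

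Four of seven are solicited. Nausea, vomiting and diarrhoea are not among the vaccine reactions in C2.1 (local reactions, low-grade fever, fatigue, myalgia, headache, malaise). So the list already reaches beyond the vaccine, but covers the drug incompletely.

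**2. Ascertainment by arm.** Table 6 gives 15 visits in Arms 1 and 3 and 9 in Arm 2. The difference of 6 is Days 1 and 2 in three rounds (2 × 3). Table 5 assesses AEs at every visit except screening, which gives 14 assessments against 8. After dosing within a round, that is Days 1, 2 and 7 against Day 7 only.

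**3. Expected number with dizziness.** Inputs: 50 in Arm 1 and 20 in Arm 3 (B6.1), and a rate p. C2.1 gives about 12% without a denominator, so reading it per participant is an assumption; 5% is taken as a lower assumed value. Expected number = n × p; chance of at least one = 1 − (1 − p)^n.

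| p | Arm 1 (n = 50) | Arm 3 (n = 20) |
|---|---|---|
| 12% | 6.0; 99.8% | 2.4; 92.2% |
| 5% | 2.5; 92.3% | 1.0; 64.2% |

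The solicited rows count none of these, by design.

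**4. Effect of incomplete unprompted capture.** Let a share s of cases be reported. The documents give no value, so take s from 25% to 75%, with p = 12%.
- Arm 1 records 50 × 0.12 × s = 1.5 to 4.5 cases.
- Arm 3 records 20 × 0.12 × s = 0.6 to 1.8 cases.
- The chance of recording none in Arm 3, (1 − 0.12s)^20, is 7.8% at full capture, 15% at s = 75% and 54% at s = 25%.

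**5. Direction of bias, Arm 1 against Arm 2.** The observed difference is s1·p1 − s2·p2. Assume p1 = 12% and a background p2 = 5%, a true difference of 7 points.
- Equal capture, s1 = s2 = 50%: 6.0 − 2.5 = 3.5 points, an understatement.
- More capture in the arm with more visits, s1 = 75% and s2 = 25%: 9.0 − 1.25 = 7.75 points, an overstatement.

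The sign depends on capture shares that nobody knows in advance.

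**6. What full capture would give.** The exact 95% interval for 6 of 50 is 4.5% to 24.3%, and for 2 of 20 it is 1.2% to 31.7%. Prompting makes ascertainment comparable; it does not make these arms large.

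The plan's only power figure for Arm 1 against Arm 2 (85% for 50% against 80%, Fisher's exact test, 50 per arm) reproduces at 85.3%. It concerns immunogenicity, and this point does not rest on it.

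**The case against.** The strongest reply is that nothing is lost. Unsolicited AEs are themselves a primary endpoint (B6.3.1), and all AEs must be recorded whatever their intensity (Appendix B 1.4.1). They are tabulated by group and MedDRA preferred term with exact intervals (Appendix B 1.6.1; SAP section 5). The same sections count general AEs, solicited and unsolicited together, in the 7-day period, and the unsolicited window contains every 7-day window. All of this stands. A reader might infer that the primary safety analysis misses dizziness; only its solicited rows do.

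A reader might also infer that Arm 1 will look closer to Arm 2 than it really is. The documents do not support that either: the extra Day 1 and Day 2 assessments in the drug arms push the other way.

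Nor does the text support saying that the list fits the vaccine and not the drug, since four of seven drug effects are on it. The 12% has no stated denominator or background rate, and C2.1 introduces the drug as a treatment for malaria, not as something given to healthy adults.

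No stated objective asks whether the vaccine worsens drug tolerability, so the contrast of Arm 1 with Arm 3 should not carry the argument. No between-arm safety test is planned. SAP 3.2 does not list solicited AEs as a primary outcome; their primary status rests on Protocol B6.3.1 and the heading of SAP section 5.

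Finally, prompting for a known drug effect in an open-label trial can itself raise reports among those who know that they took the drug. That is a real cost. It does not remove the case for asking every arm the same question.

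**Conclusion.** The omission is real, and its consequence is limited. Three of the seven drug effects that the protocol names are unprompted, including dizziness, the only one it puts above 10%. Calling dizziness the commonest is a fair reading of C2.1, not its wording. These events can still enter the primary safety data and the combined 7-day tables, but through free text and an open question, on another grading scale, and with 14 AE assessments in Arms 1 and 3 against 8 in Arm 2. The between-arm comparison for them therefore rests on unequal, unprompted ascertainment, and the net direction of bias is unknown.

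If 12% is per participant, the events concerned number about 6 of 50 and 2.4 of 20; at an assumed 5%, 2.5 and 1.0. The lists and the visit schedule are read directly from the documents. The rates per participant, the capture shares and the background rate are assumptions. This is a worthwhile low-cost improvement, not a flaw that invalidates the safety analysis.

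**What to change.** Add dizziness, abdominal pain and disturbed sleep to the systemic solicited list in Table 8, Appendix B 1.2.3 and the diary card, for all three arms, on the same self-assessment scale and in the same window as the other terms. Add matching rows by arm to the SAP's solicited-AE tabulation.

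If diary cards are already in use, pre-specify in the SAP that these three terms are tabulated separately by arm in one common window, with a note that visit frequency differs between arms.

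Two sets of passages need reconciling at the same time:
- Appendix B 1.7 applies different individual stopping rules to systemic solicited and to unsolicited AEs. The former refers to vaccination or drug administration; the latter requires relation to vaccination. Moving a term onto the list changes which rule covers it, so the sponsor should reconcile that section with the revised list. No clinical rule is proposed here.
- SAP section 5 restricts the safety analysis to those allocated to vaccination, yet its Table 4 has a No Vaccine column, and Arm 3 has no vaccination date from which to count the 7 days.

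The cost is three lines on a paper diary, with the matching CRF fields and table rows. The downsides are slightly more diary burden, possible prompted over-reporting in an open-label trial, and an overall percentage with any solicited AE that is less comparable with earlier R21 trials. The rows for individual symptoms stay comparable.

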All potential volunteers will have a screening visit, which may take place up to 7 days prior to enrolment. Once informed consent is given, a screening number will be assigned in sequential order. Screening numbers will be issued consecutively (e.g. R21-001, R21-002, R21-003 etc.). This will be recorded in the Case Screening Form, together with the demographic information and procedures performed to determine eligibility. Screening procedures indicated in the schedule of procedures (Table 5) will be undertaken. If a screening haematology or biochemistry test result is out of the normal range, it may be repeated to ensure it is not a single occurrence. If an abnormal finding at screening is considered to be clinically significant, the volunteer will be informed, appropriate medical care arranged with the permission of the volunteer and the volunteer will be excluded from the study. In the unlikely event that a volunteer is found to have malaria or anaemia, the volunteer will be treated according to national guidelines and will be excluded from participating in the study.

B6.4.3 Enrolment and Baseline Assessment

All inclusion and exclusion criteria will be checked before enrolment in the study. Physical examination will be performed. Any new medical issues or symptoms that have arisen will be assessed. Blood will be collected for baseline *P. falciparum* test, clinical hematology and biochemistry. Blood will be collected and stored for measurement of antibodies against *P. falciparum* circumsporozoite (anti-CS antibody) until shipment to the reference laboratory. Urine will be collected from women of child-bearing potential for immediate pregnancy test.

If the interval between screening and enrolment is 7 days or less, the screening test results (*P. falciparum* test, haemoglobin, biochemistry, and urine pregnancy test) can be used for enrolment evaluation. In such cases, the tests (*P. falciparum* test, clinical hematology, biochemistry, and urine pregnancy test) will not be repeated at the baseline (Month 0 / Day 0) visit.

If all inclusion criteria are fulfilled and none of the exclusion criteria apply, the patient will be enrolled into the study and a case record form (CRF) specific to each participant completed. Regimen allocation and administration of the vaccine will be on Day 0 Month 0. The randomization lists will

**Research Proposal Submission Form
for a study involving human subject enrollment WITH
specimen collection**

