- Serology to quantify and characterise the binding properties of antibodies to the vaccine components (full length R21, CS C-term, NANP and HBsAb), including total IgG, IgG avidity, subclasses and isotypes.
- Functional assays to measure antibody function, such as inhibition of sporozoites invasion and systems serology assays

**Research Proposal Submission Form
for a study involving human subject enrollment WITH
specimen collection**

Document No.: FTM ECF-033-01

Page 27 of 52

- Flow cytometry assays to enumerate and functionally characterise immune cell populations such as effector and memory T cells (e.g. CD4+ and CD8+), T follicular helper cells, regulatory T cells, B cells, plasma cells and dendritic cells
- Enumeration of antibody-secreting cells (e.g. B and plasma cells)
- Assays to assess presence or absence of other factors affecting vaccine immunogenicity, such as antibodies against viral pathogens including cytomegalovirus.
- Other ELISA assays for immunity to malaria that may be relevant to prior malaria exposure and be used to predict vaccine immunogenicity.

Genetic tests for determination of associated genes that can have an impact on vaccination. N.B. Specific consent genetic testing will be sought through an additional question on the ICF to make clear to participants that consent for genetic testing does not affect participation in the clinical trial.

Drug levels

The study investigates two questions regarding the potential interactions between antimalarial drugs and vaccines.

- 1) Does the co-administration of antimalarial drugs with vaccines influence vaccine antibody levels
- 2) Does the co-administration of antimalarial drugs with vaccines influence drug levels.

The second question will be addressed for piperaquine only. Piperaquine levels will be assessed during each round (M0, M1, and M2) on Day 0, 1, 2, and 7 (at M0D0, drug level will be assessed, if additional data are required). (Table 9.) Additional drug level assessment for primaquine will be done if additional data are required.

Table 9. Pharmacokinetic blood sampling time.

Month(s)	Day(s)	PK*
M0	Day 0	x
	Day 1	x
	Day 2	x
	Day 7	x
M1	Day 0	x
	Day 1	x
	Day 2	x
	Day 7	x
M2	Day 0	x
	Day 1	x

**Research Proposal Submission Form
for a study involving human subject enrollment WITH
specimen collection**

Document No.: FTM ECF-033-01

Page 28 of 52

Month(s)	Day(s)	PK*
	Day 2	x
	Day 7	x

Remark:

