**Research Proposal Submission Form
for a study involving human subject enrollment WITH
specimen collection**

Document No.: FTM ECF-033-01

Page 30 of 52

- Participants vaccinated with the wrong study agent (non-compliance with the randomization code)
- Participants excluded from the intention-to-treat analysis.
- No interim analysis is planned.

B6.7.5 Analysis of baseline characteristics

The demographic characteristics of enrolled participants will be compared by study group.

B6.7.6 Analysis of immunogenicity

The serum anti-CS antibody titre and avidity

The main analyses will involve the serum anti-CS antibody titre and avidity. These parameters will be measured at baseline and then at follow-up times longitudinally. During statistical analysis, we will assess whether a participant had a titre that is greater than 4 times that of the participant's baseline titre. Then we will compute the number of participants who had a titre of greater than 4 times their baseline titres and obtain a proportion of these for each group. These proportions of participants with >4-fold rise in titre from baseline will be compared between arms at each follow-up time. A Fisher's exact test will be used to compare the proportions of participants with >4-fold rise in titre from baseline between groups at each follow-up. These proportions will also be summarised graphically by arm to visually assess the differences between arms over-time. This will help to visually assess whether time modifies the effect of group.

Furthermore, the absolute titre values will be analysed and compared between groups. Since the distribution of these titre values will likely be highly skewed overtime, these values will be log-transformed and compared between arms at the different follow-up times. In order to revert back to the original scale (taking exponentials), the Geometric Mean Ratios (GMR) of the titres will be the measures of effect of interest that will be used to compared the log-transformed titres between the arms. The 95% confidence intervals for the Geometric Mean Ratios will be presented. The mean titre trends (on log-scale) over time will also be plotted by arm to assess whether there is a difference in trends of the titres between arms over time.

Tests of significance will be performed at 5% significance level. Analyses will be performed in Stata version 17 or higher. A separate detailed Statistical Analysis plan will be developed, finalized and signed before databased lock.

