4.1.7 ANALYSIS OF IMMUNOGENICITY

The serum anti-CS antibody titre and avidity responses for each treatment arm will be compared to the titre before vaccine administration as outlined in tables 2a, 2b, 3a and 3b below. In addition, immunology will be analyzed and compared in terms of the potential parameters using appropriate statistics according to the data structure in which data will be presented to the statistician. While the final choice of immunologic assays will be determined at a later stage the may include the following:

- *Plasmodium falciparum*. Circumsporozoite Protein. (NANP)6 Ab.IgG
- *Plasmodium falciparum*. Circumsporozoide Protein. (NANP)6 Ab.IgG Avidity
- *Plasmodium falciparum*. anti-C-Term Circumsporozoide Ab.IgG
- *Plasmodium falciparum*. anti-C-Term Circumsporozoide Ab.IgG avidity
- *Plasmodium falciparum*. Circumsporozoite Full length (N+C-Terminal)
- *Plasmodium falciparum*. anti-full length CSP Ab.IgG avidity

The serum anti-CS antibody titre -Proportion in study group with >4-fold rise in titre from baseline to: One month after first dose; One month after second dose; One month after the third dose; Six Months after the first dose for all groups.

Table 3ai. *Plasmodium falciparum*. Circumsporozoite Protein.(NANP)6 Ab.IgG

ARM	1 month after 1 st dose n (%)	1 month after 2 nd dose n (%)	1 month after 3 rd dose n (%)	6 months after 1 st dose n (%)
R21/Matrix-M™ + DHA-PIP + SLD-PQ				
R21/Matrix-M™				
No vaccine				

Table 3aii. *Plasmodium falciparum*. anti-C-Term Circumsporozoide Ab.IgG

ARM	1 month after 1 st dose n (%)	1 month after 2 nd dose n (%)	1 month after 3 rd dose n (%)	6 months after 1 st dose n (%)
R21/Matrix-M™ + DHA-PIP + SLD-PQ				
R21/Matrix-M™				
No vaccine				

Table 3aiii. *Plasmodium falciparum*. Circumsporozoite Full length (N+C-Terminal)

ARM	1 month after 1 st dose n (%)	1 month after 2 nd dose n (%)	1 month after 3 rd dose n (%)	6 months after 1 st dose n (%)
R21/Matrix-M™ + DHA-PIP + SLD-PQ				
R21/Matrix-M™				
No vaccine				

AVIDITY

Avidity -Proportion in study group with >4-fold rise from baseline to: One month after first dose; One month after second dose; One month after the third dose; Six months after the first dose for all the three groups. These will be summarised in tables 2bi to 2bii as follows:

Table 3bi. *Plasmodium falciparum*. Circumsporozoide Protein.(NANP)6 Ab.IgG Avidity

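### The Arm 1 v Arm 2 titre ratio has no stated model; prespecifying adjustment for baseline titre costs almost nothing and may narrow its interval

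*Protocol*

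**What the plan says.** Protocol B6.7.6 states of titre and avidity: "These parameters will be measured at baseline and then at follow-up times longitudinally". It then plans two comparisons between arms.

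- **Responders.** "These proportions of participants with >4-fold rise in titre from baseline will be compared between arms at each follow-up time", by Fisher's exact test. Each participant's own baseline is built into this outcome.
- **Absolute titres.** "these values will be log-transformed and compared between arms at the different follow-up times", and "the Geometric Mean Ratios (GMR) of the titres will be the measures of effect of interest", with 95% confidence intervals. No model, covariate or repeated-measures analysis is named. Mean log titres over time are plotted by arm.

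The baseline sample is available. At enrolment (Protocol B6.4.3), "Blood will be collected and stored for measurement of antibodies against" the circumsporozoite protein. Protocol Table 5 shows the immunology draw at Month 0 Day 0 with no restriction by arm, whereas piperaquine levels are limited to Groups 1 and 3.

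SAP 4.1.7 says that "titre and avidity responses for each treatment arm will be compared to the titre before vaccine administration". It also uses baseline in the tables of >4-fold rise and in the seropositivity cut-off (baseline mean plus 2 SD). Its geometric-mean shells (Tables 4ai to 4biii) hold one value with a 95% CI per arm and visit. There is no Arm 1/Arm 2 ratio and no model for one. Otherwise the choice of statistics is left to the form in which the data reach the statistician.

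**The concern.** One stated aim is to confirm that the antimalarials do not reduce the vaccine's immunogenicity. A claim of no reduction is only as good as the interval around the Arm 1/Arm 2 ratio, and there are 50 participants per arm. A measured baseline that predicts the outcome is an inexpensive way to narrow that interval, and the plan does not say whether it will be used.

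The silence matters in a second way. The trial is open-label and the SAP leaves the method open, so the choice between an adjusted and an unadjusted ratio could be made after results are seen.

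**Working it through.** **1. The plan's own figure.** Protocol B5.3 gives 85% power for 50% v 80% responders with 50 per arm, by Fisher's exact test. The plan says "Tests of significance will be performed at 5% significance level" without stating sidedness; two-sided is assumed here. Exact enumeration over both binomials gives 0.853, so the figure reproduces. It belongs to the responder comparison. Neither document gives a power or precision figure for the GMR.

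**2. Inputs for the GMR.**
- n = 50 per arm (Protocol Table 1).
- Correlation r of baseline with follow-up log titre: not given; 0 to 0.5 assumed.
- SD of log titre: not given; 0.4 on the log10 scale assumed for illustration, with 0.3 to 0.6 as the range.

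**3. Formulas.** Adjusting for log baseline multiplies the residual variance by 1 − r², so the CI half-width is multiplied by about √(1 − r²) and the equivalent sample size is 50/(1 − r²) per arm. The unadjusted CI factor is exp(t × SD × ln 10 × √(2/50)). At SD 0.4 that is exp(1.984 × 0.921 × 0.20) = 1.44. The power column takes the effect that the unadjusted test detects with 80% power (98 df unadjusted, 97 df adjusted).

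| r | 1 − r² | Half-width ratio | Equivalent n per arm | Power | CI factor (SD 0.4) |
|---|---|---|---|---|---|
| 0 | 1.00 | 1.000 | 50.0 | 80.0% | 1.441 |
| 0.1 | 0.99 | 0.995 | 50.5 | 80.4% | 1.439 |
| 0.2 | 0.96 | 0.980 | 52.1 | 81.6% | 1.431 |
| 0.3 | 0.91 | 0.954 | 54.9 | 83.6% | 1.417 |
| 0.5 | 0.75 | 0.866 | 66.7 | 89.9% | 1.372 |

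Across SDs of 0.3 to 0.6, the unadjusted CI factor runs from 1.32 to 1.73. At r = 0.5 it runs from 1.27 to 1.61.

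**4. Cost of estimating the slope.** The formula omits this. In 20,000 simulated trials per value of r, the ratio of adjusted to unadjusted standard error was 1.005 at r = 0, 0.960 at r = 0.3 and 0.873 at r = 0.5. The cost is therefore about 0.5%. At r = 0.1 it roughly cancels the gain (0.995 × 1.005 = 1.000). Type I error was close to 5% (0.047 to 0.049) with or without adjustment.

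**5. Chance imbalance.** The baseline difference between two arms of 50 has an SD of √(2/50) = 0.20 baseline SDs. It moves the unadjusted log ratio by r × 0.20, that is 0.06 outcome SDs at r = 0.3 and 0.10 at r = 0.5. The unadjusted standard error is itself 0.20 outcome SDs, and (0.06/0.20)² = 0.09 = r². The shift is the same r² share of variance already counted in step 3.

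**The case against.** The strongest reply is that nothing in the plan is wrong. No passage says that the ratio will be unadjusted; that would be an inference from silence. Randomisation makes the comparison valid either way. The first-listed comparison, which also sized Arms 1 and 2, already works relative to each participant's own baseline. The gain rests on a correlation that nobody has documented. Participants must test malaria-negative at entry and infection during the trial is thought highly unlikely (Protocol B5.2.2 and B6.7.3), so baselines may show little spread and r may be small. All of this stands, and it limits the point to efficiency and prespecification. It does not supply the missing model.

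A reader might infer four stronger things that the documents do not support.

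- **Chance baseline imbalance is a separate bias.** It is not; step 5 shows that the unadjusted standard error already contains it.
- **The plan expects baseline anti-CS titre to predict response.** The nearest line, in Protocol B6.6.1, is "Other ELISA assays for immunity to malaria that may be relevant to prior malaria exposure and be used to predict vaccine immunogenicity". It concerns other assays, run at the investigators' discretion, and gives no correlation for anti-CS titre.
- **Visit-by-visit analysis loses much.** With complete data, a repeated-measures model with unstructured covariance gives essentially the same contrast at each visit. The per-protocol set, which is the main one for immunogenicity (SAP 4.1.4), excludes participants who miss the blood-sampling schedule. The benefit is mainly for missing visits in the intention-to-treat analysis.
- **Variable visit timing needs correcting in the main model.** Protocol Table 7 lets Month 6 fall 91 to 133 days after dose 3 (21 + 70 to 35 + 98). The windows are the same in both arms, however, and SAP 3.1 already reports results with and without out-of-window visits. Days since last dose is also a post-randomisation variable that arm could affect.

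**Conclusion.** The concern holds as a gap in specification with a possible, modest loss of precision. Neither document names a model or covariate for the Arm 1 v Arm 2 ratio of absolute titres, although baseline titre is measured in everyone.

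The size depends on the assumed r. Adjustment makes the interval about 0.5% wider at r = 0, leaves it about unchanged at r = 0.1, and narrows it by about 5% at r = 0.3 and 13% at r = 0.5. If most baselines are at the assay floor, the gain is about nil. The planned comparison is not biased, and the stated sample size and its 85% power are unaffected. The change is worth making because it could help, costs almost nothing, and settles the method before the data are seen.

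**What to change.** In SAP 4.1.7, prespecify the Arm 1/Arm 2 GMR with 95% CI at Months 1, 2, 3 and 6 from a linear model of log titre on arm and log baseline titre. Either of two forms will do: ANCOVA at each visit, or one repeated-measures model with arm × visit, baseline × visit and unstructured covariance. The second mainly helps where visits are missing in the intention-to-treat analysis. State the value assigned to baselines below the assay limit, for example half the limit. Add a row or table for the ratio, since the present shells have none.

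Keep the Fisher responder comparison and its plot by arm. The plot checks visually whether the arm difference in responder proportions changes over time, and a log-titre model does not replace that. Actual days since last dose is at most an optional sensitivity analysis.

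The cost is SAP wording, one standard model in Stata, and one to a few extra parameters. No new samples or assays are needed.
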